21.2 Appendix II - Psoriasis Area and Severity Index (PASI)

To be assessed by the investigator:

The Psoriasis Area and Severity Index (PASI) is a system used for assessing and grading the severity of psoriatic lesions and their response to therapy. The PASI produces a numeric score that ranges from 0-72.

The severity of the disease is calculated by scoring the signs of the disease (erythema, induration and scaling) for each of the following 4 body-regions: head (h), trunk (t), upper extremities (u) and lower extremities (l). The scoring system for the signs of the disease is: 0 = none, 1 = slight, 2 = moderate, 3 = severe, 4 = very severe.

The scale for estimating the area of involvement for psoriatic lesions is outlined below.

0	=	No involvement
1	=	1% to 9% involvement
2	=	10% to 29% involvement
3	=	30% to 49% involvement
4	=	50% to 69% involvement
5	=	70% to 89% involvement
6	=	90% to 100% involvement

To help with the area assessment, the following conventions should be noted:

- a. The neck is considered part of the head
- b. The axillae and groin are part of the trunk
- c. The buttocks are part of the lower extremities

The PASI formula is:

$$\text{PASI} = 0.1(E_h + I_h + S_h) A_h + 0.3 ((E_t + I_t + S_t) A_t + 0.2 (E_u + I_u + S_u) A_u + 0.4 (E_l + I_l + S_l) A_l$$

where E = erythema, I = induration , S = Scaling, and A = area.

(33)

21.3 Appendix III: Palmoplantar Pustulosis Psoriasis Area and Severity Index (PPPASI)

To be assessed by the investigator:

The severity of the disease is calculated by scoring the signs of the disease (erythema, pustules and scaling) for each of the following 4 body-regions: right palm (RP), left palm (LP), Right Sole (RS) and Left Sole (LS). The scoring system for the signs of the disease is: 0 = none, 1 = slight, 2 = moderate, 3 = severe, 4 = very severe.

The scale for estimating the area of involvement for psoriatic lesions is outlined below.

0	=	No involvement
1	=	1% to 9% involvement
2	=	10% to 29% involvement
3	=	30% to 49% involvement
4	=	50% to 69% involvement
5	=	70% to 89% involvement
6	=	90% to 100% involvement

Body region	Erythema (E)	Pustules / (P) vesicles	Scaling (D) (desquamation)	Area score (A) (based on true Area %) *
Right palm (RP)	0 = none 1 = slight 2 = moderate 3 = severe 4 = very severe	0 = none 1 = slight 2 = moderate 3 = severe 4 = very severe	0 = none 1 = slight 2 = moderate 3 = severe 4 = very severe	0 = no Involvement 1 = >0 - < 10% 2 = 10 - <30% 3 = 30 - <50% 4 = 50 - <70% 5 = 70 - <90% 6 = 90 - 100%
Left palm (LP)	0 = none 1 = slight 2 = moderate 3 = severe 4 = very severe	0 = none 1 = slight 2 = moderate 3 = severe 4 = very severe	0 = none 1 = slight 2 = moderate 3 = severe 4 = very severe	0 = no Involvement 1 = >0 - < 10% 2 = 10 - <30% 3 = 30 - <50% 4 = 50 - <70% 5 = 70 - <90% 6 = 90 - 100%
Right sole (RS)	0 = none 1 = slight 2 = moderate 3 = severe 4 = very severe	0 = none 1 = slight 2 = moderate 3 = severe 4 = very severe	0 = none 1 = slight 2 = moderate 3 = severe 4 = very severe	0 = no Involvement 1 = >0 - < 10% 2 = 10 - <30% 3 = 30 - <50% 4 = 50 - <70% 5 = 70 - <90% 6 = 90 - 100%
Left sole (LS)	0 = none 1 = slight	0 = none 1 = slight	0 = none 1 = slight	0 = no Involvement

	2 = moderate 3 = severe 4 = very severe	2 = moderate 3 = severe 4 = very severe	2 = moderate 3 = severe 4 = very severe	1 = >0 - < 10% 2 = 10 - <30% 3 = 30 - <50% 4 = 50 - <70% 5 = 70 - <90% 6 = 90 - 100%
--	---	---	---	---

The PPPASI score is calculated using the formula:

PPPASI = 0.2 (ERP + PRP + DRP) ARP + 0.2 (ELP + PLP + DLP) ALP + 0.3 (ERS + PRS + DRS) ARS + 0.3 (ELS + PLS + DLS) ALS

(36)

21.4 Appendix IV - Physician's Global Assessment (PGA)

To be assessed by the investigator:

Assessment of the average severity of all skin lesions at the assessment timepoint according to the following categories:

Score	Category	Description
0	Clear	Plaque elevation = 0 (no elevation over normal skin) Scaling = 0 (no evidence of scaling) Erythema = 0 (except for residual hyperpigmentation/hypopigmentation)
1	Almost Clear	Plaque elevation = ± (possible but difficult to ascertain whether there is a slight elevation above normal skin) Scaling = ± (surface dryness with some desquamation) Erythema = ± (faint, diffuse pink or slight red coloration)
2	Mild	Plaque elevation = slight (slight but definite elevation, typically edges are indistinct or sloped) Scaling = fine (fine scale partially or mostly covering lesions) Erythema = mild (light red coloration)
3	Moderate	Plaque elevation = marked (marked definite elevation with rough or sloped edges) Scaling = coarser (coarser scale covering most or all of the lesions) Erythema = moderate (definite red coloration)
4	Severe	Plaque elevation = marked (marked elevation typically with hard or sharp edges) Scaling = coarser (coarse, non tenacious scale predominates covering most or all of the lesions) Erythema = severe (very bright red coloration)

Adapted from (37)

21.5 Appendix V - Dynamic Hand and Feet (H&F) PGA

To be assessed by the investigator:

Assessment of the global improvement of the H&F Psoriasis lesions compared from baseline to the assessment timepoint, reflecting a global consideration of at least erythema, scaling, plaque thickness, fissuring and postulation according to the following categories:

Category	Percentage Improvement	Category Description
Cleared (0)	100%	Remission of all clinical signs and symptoms as compared with baseline, except for residual manifestations such as mild erythema
Excellent (1)	75% - 99%	Improvement of all clinical signs and symptoms as compared with baseline, except for residual manifestations such as mild erythema
Good (2)	50% - 74%	Improvement of all clinical signs and symptoms as compared with baseline
Fair (3)	25% - 49%	Improvement of all clinical signs and symptoms as compared with baseline
Slight (4)	1% - 24%	Improvement of all clinical signs and symptoms as compared with baseline
Unchanged (5)		Clinical signs and symptoms unchanged from baseline
Worse (6)		Clinical signs and symptoms deteriorated from baseline

(38)

21.6 Appendix VI - Hand and Feet (H&F) PGA

To be assessed by the investigator:

Assessment of the average severity of the H&F Psoriasis skin lesions at the assessment timepoint according to the following categories:

Score	Category	Category Description
0	Clear	No signs of plaque psoriasis on the hands and / or feet
1	Almost Clear	Just perceptible erythema and just perceptible scaling on the hands and/ or feet
2	Mild	Light pink erythema with minimal scaling and with or without pustules on the hands and / or feet
3	Moderate	Dull red, clearly distinguishable erythema with diffuse scaling, some thickening of the skin, with or without fissures, and with or without pustule formation on the hands and / or feet
4	Severe	Deep/ dark red erythema with clearly obvious and diffuse scaling and thickening, and numerous fissures with or without pustule formation on the hands and / or feet

(28)

[figure not shown]
21.7 Appendix VII - Visual Analogue Scale (VAS)

To be filled out by the patient:

Scale will be exactly 100mm in length with a statement at each end representing one extreme of the dimension being measured (e.g. intensity of itch, discomfort or pain). After short explanation by the treating physician, patient will put a vertical bar at that point of the scale which reflects the current patients' subjective status best.

[figure not shown]
Patient's assessment of pruritus / itch

On average, how much itch have you had because of your condition in the past week?

Patient's assessment of skin discomfort / pain

On average, how much skin discomfort / pain have you had because of your condition in the past week?

Please note: VAS above is not drawn to scale and is for illustrative purpose only.

(39)

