Ethical Considerations	
This study will be conducted in accordance with applicable laws and regulations including, but not limited to, the ICH E6 guideline and the ethics principles that have their origins in the Declaration of Helsinki. The independent ethics committee and the competent authority must review and approve the study before any patients are enrolled. Consent must be obtained from the patient using the approved informed consent form (ICF) before any procedures specified in the protocol are performed.
 
The data acquisition meets all requirements of data protection for each individual patient, since all patient-related documentation can only be identified by a patient identification number. All personal information of the patient is accessible only to the treating physician.

Study Flow Chart

Phase	Screening	Treatment Phase					Early Termination
		V2 Baseline	V3	V4	V5 End of Study		
Visits	V1						
Week	-4 -- 1	0	4	12	20		
Day	-28 -- 1	0	28 ± 4	84 ± 4	140 ± 7		
In- / exclusion criteria	x	x	-	-	-	-	-
Pregnancy test ¹	x	x	x	x	x	x	
Informed consent	x	-	-	-	-	-	
Demography, educational status	x	-	-	-	-	-	
Medical and psoriasis history, prior medication	x	-	-	-	-	-	
PsA, comorbidity	x	x	-	x	x	x	
Concomitant medications	x	x	x	x	x	x	
Nicotine anamnesis	x	-	-	-	x	-	
Physical examination incl. weight and height ² (BMI)	x	x	-	-	x	x	
Vital signs ³	x	x	x	x	x	x	
Results of routine blood test / urinalysis available ⁴	x	-	-	-	-	-	
Investigator assessments							
PASI	-	x	x	x	x	x	
PPPASI	x ⁵	x	x	x	x	x	
PGA	-	x	x	x	x	x	
H&F PGA	-	x	x	x	x	x	
Dynamic H&F PGA	-		x	x	x	x	
Pustules count	-	x	x	x	x	x	
Patient reported outcomes							
VAS (pruritus / itch and discomfort / pain) on hands and feet	-	x	x	x	x	x	
DLQI	-	x	-	x	x	-	
Photographs ⁶ (optional)	-	x	-	-	x	-	
Serum and plasma	-	x	x	x	x	x	
Biopsies ⁷ (optional sub-study)	-	x	-	-	x	x	
Documentation for drug accountability and treatment compliance	-	x	x	x	x	x	
Medication dispensing ⁸	-	x	x	x	-	-	
Return of study medication	-	-	x	x	x	x	
AEs / SAEs	x	x	x	x	x	x	
Reason for discontinuation						x	

1. Urine pregnancy test for female patients of childbearing potential
2. Only at V1: height
3. Sitting blood pressure and pulse rate
4. Within the ranges given in the exclusion criteria **not older than 8 weeks** prior to screening
5. For inclusion PPPASI must be ≥ 12
6. From both hands and feet (optional)
7. Two lesional biopsies from feet or hands (optional)
8. Including instructions for medication intake

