7.2 Secondary Objective(s)

The secondary objectives of the study are:

- To evaluate an improvement of PPPASI at all assessment times compared with baseline in moderate to severe chronic palmoplantar pustulosis under apremilast therapy.
- To evaluate differences during the treatment with apremilast in life quality assessment measures: Dermatology Life Quality Index (DLQI) at all assessment times compared with baseline
- To evaluate safety of apremilast in patients with moderate to severe palmoplantar pustulosis

Exploratory objectives are:

- Time course of Hand and Feet Physician Global Assessment (H&F PGA) at all assessment times.
- Pustules count 50 response and Pustules count 75 response, defined as a 50% and 75% decrease in Pustules count from baseline, during the 20 weeks treatment period
- To evaluate differences in the mean change from baseline at all assessment times of VAS pruritus / itch, VAS discomfort / pain at all assessment times relatively to day 0 (baseline)
- To evaluate changes in Psoriasis Area Severity Index (PASI), Physician Global Assessment (PGA) and dynamic H&F PGA if plaque psoriasis is present between baseline and all assessment times
- To explore the effect of apremilast on immunological markers in serum / plasma
- To explore the effect of apremilast on immunological markers in skin biopsies (sub-study, see Section 12.1.10.2)

8 Study Design

This study will be conducted in accordance with applicable laws and regulations including, but not limited to, the ICH E6 guideline 'Note for Good Clinical Practice' (CPMP/ICH/135/95) (2) based on the principles of the Declaration of Helsinki (3). The study will be duly conducted in compliance with the Medicinal Products Act (Arzneimittelgesetz AMG), (§§ 40-42) (1). An independent ethics committee and the competent authority must review and approve the study before any patients are enrolled.

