9.1.1 Inclusion Criteria

- Male and female patients aged 18 years or more at screening visit.
- Patients with chronic PPP (disease history of at least 6 months of diagnosis), who are eligible for treatment with systemic therapy defined as having PPP inadequately controlled by topical treatment and / or phototherapy and / or previous systemic therapy
- Patients with chronic moderate to severe PPP defined as patients with a PPPASI ≥ 12 with or without concomitant plaque-type psoriasis
- Negative result of a urine pregnancy test taken at screening and at baseline for all women, except those who are surgically sterile or at least 1 year postmenopausal (i.e. at least 12 consecutive months with amenorrhea without other known or suspected medical cause)
- Willingness and capability of using a highly effective contraceptive measures from Screening visit until the end of at least one menstrual cycle (but not less than 28 days) following discontinuation of apremilast as defined below:
 - Female patient of childbearing potential (fertile, following menarche and until becoming post-menopausal unless permanently sterile) using a highly effective method of contraception OR female patients of non-childbearing potential (surgically sterilized [e.g. hysterectomy, bilateral salpingectomy and bilateral oophorectomy] or post-menopausal)
 - Male patient, and their female partner of childbearing potential, using a highly effective method of contraception
 - Adequate contraceptive method defined as:
 - A method with less than 1% failure rate (e.g. permanent sterilization, hormone implants, hormone injections, some intrauterine devices, or vasectomized partner)
- OR
 - The use of two methods of contraception (e.g. one barrier method [condom, diaphragm or cervical/vault caps] with spermicide and one hormonal contraceptive [e.g. combined oral contraceptives, patch, vaginal ring, injectables and implants])
- Patient is capable of understanding and giving written, voluntary informed consent before study screening.
- Willingness and capability of complying with all study procedure requirements, as per the Investigator's judgment (e.g. patient able to swallow the apremilast tablets, blood sampling).

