11.2.3 Visit 3 - (Week 4, Day 28 ±4)

- A urine pregnancy test (β -hCG) will be performed in females with childbearing potential.
- Vital signs will be assessed.
- Concomitant medication will be documented.
- The patient will be interviewed concerning the occurrence of AEs.
- Serum and plasma samples will be taken.
- The investigator will
 - ask the patient to rate their pruritus and pain on hands and feet using the VAS.
 - assess the PASI, PPPASI, PGA, H&F PGA, dynamic H&F PGA and pustules count.
- Study medication will be collected for drug accountability and documentation for treatment compliance. Further study medication will be dispensed. The patient will be reminded and re-instructed on when and how to take the study medication.
- The patient will be instructed to return all study medication to the next visit.
- A return appointment for the next visit will be scheduled.

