12.1.8 Visual Analogue Scale (VAS)

A VAS is used to assess pruritus (itch) and discomfort / pain on hands and feet.

The patient will be asked to place a vertical stroke on a 100 mm VAS on which the left-hand boundary represents either no pruritus (itch) or discomfort / pain, and the right-hand boundary represents either pruritus (itch) or discomfort / pain as severe as can be imagined. The distance from the mark to the left-hand boundary will be recorded.

For more details refer to Appendix 21.7.

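### The VAS form in Appendix VII gives two recall periods, and its questions do not name the hands and feet that the protocol says it measures (minor; exploratory assessment only)

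*Protocol*

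**What the plan says.** **Time frame.** Appendix VII (Section 21.7) states that, after a short explanation by the treating physician, the "patient will put a vertical bar at that point of the scale which reflects the current patients' subjective status best". The itch question on the same form reads "On average, how much itch have you had because of your condition in the past week", and the second question reads "On average, how much skin discomfort / pain have you had because of your condition in the past week". Section 12.1.8 describes the 100 mm line and its end points but gives no recall period.

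**Body site.** Section 12.1.8 opens with "A VAS is used to assess pruritus (itch) and discomfort / pain on hands and feet". The flow chart row is labelled "VAS (pruritus / itch and discomfort / pain) on hands and feet", and the efficacy paragraph of the synopsis names the same site. From baseline onwards, the visit descriptions in Sections 11.2.2 to 11.2.6 tell the investigator to "ask the patient to rate their pruritus and pain on hands and feet using the VAS". The two questions name no site.

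**Population and status.** Section 9.1.1 admits patients with PPPASI of at least 12 "with or without concomitant plaque-type psoriasis". The VAS appears among the exploratory objectives in Section 7.2: "To evaluate differences in the mean change from baseline at all assessment times of VAS pruritus / itch, VAS discomfort / pain". It is in none of the endpoint lists (Protocol Section 8.2; SAP Sections 3.1 to 3.3).

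**The concern.** A symptom rating needs one period and one site. Here the instruction and the questions point to different periods, and the questions leave open a site that the rest of the protocol fixes. A patient who answers the questions literally can give a rating that is not the one Section 12.1.8 defines.

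Two things could follow. A patient or physician may treat the mark as a rating of the moment, while others treat it as a weekly average. A patient with plaque psoriasis may count itch or pain from plaques elsewhere on the body. Section 6.1 states that apremilast is effective in plaque psoriasis, so body symptoms may change on treatment for reasons unrelated to the palms and soles. With no control arm, nothing in the design would separate the two.

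The measure has some weight for patients. Section 6.1 describes itch as often serious, and pain as keeping patients from walking or working. The VAS is the only patient-reported symptom score that the protocol defines for hands and feet. The first DLQI question asks about the skin in general, and the dynamic H&F PGA, which also mentions symptoms, is rated by the physician.

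**Working it through.** The point concerns wording and depends on no power or sample-size figure. The plan states no figure to reproduce, so the texts are set side by side.

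| Source | Period | Site |
|---|---|---|
| Appendix VII, marking instruction | current status | none |
| Appendix VII, itch question | past-week average | none (the condition) |
| Appendix VII, discomfort / pain question | past-week average | none (the condition) |
| Section 12.1.8 | none | hands and feet |
| Synopsis and flow chart | none | hands and feet |
| Visit descriptions, 11.2.2 to 11.2.6 | none | hands and feet |

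**Step 1, period.** The contradiction lies within Appendix VII. No other section states a period, so nothing else in the protocol resolves it.

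**Step 2, site.** Every place that defines or schedules the VAS says hands and feet. The questions put to the patient do not.

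**Step 3, who can be affected.** The period conflict can touch any patient. The site gap matters only for patients with psoriasis symptoms outside the hands and feet. Such patients may enrol, but the documents do not say how many are expected.

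**Step 4, effect on change from baseline.** If a patient uses one reading throughout, the change is coherent for that patient but may be a different quantity from another patient's, which adds noise. If the reading differs between baseline and a later visit, that difference enters the change score.

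**Step 5, where the score is used.** The primary and secondary endpoints use PPPASI, DLQI and safety data. Protocol Section 14.6 has a sentence on Wilcoxon tests for other endpoints that could be read to include the VAS. SAP Section 6.3.7, however, places exploratory analyses outside the statistical analysis, and SAP Appendix 1 has no VAS table or listing.

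**Step 6, size of the site effect.** Let p be the share of patients with plaque psoriasis elsewhere, w the weight (0 to 1) that their mark gives to body symptoms, d the fall in body itch and h the fall in hand and foot itch, in mm. The mean reported fall then differs from the true hand and foot fall by

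shift = p × w × (d − h).

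The documents give none of these inputs. Assume p = 0.20 to 0.40, d = 30 mm and h = 0:

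- w = 1: 0.20 × 30 = 6 mm; 0.40 × 30 = 12 mm
- w = 0: 0 mm

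Under these assumptions the range is 0 to 12 mm on a 100 mm scale. If hand and foot itch fell more than body itch (h above d), the sign would reverse. The formula does not cover the period conflict, for which the documents offer no basis for a figure.

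**The case against.** The strongest reply is that the practical risk is small.

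- **Little depends on the VAS.** It supports an exploratory objective, is not a listed endpoint, and has no planned output in the SAP. This stands and sets the severity.
- **The patient is asked about the past week.** Both questions agree on that. The word pointing to the present occurs once, in a procedural sentence about the patient, and the content of the physician's explanation is not given. Section 12 also asks that the same investigator assess a patient throughout where possible, which should limit drift between visits. This lowers the risk but leaves the form inconsistent, and the explanation may still vary across about 5 sites.
- **The site is covered at the visit.** Investigators are told to ask about hands and feet each time the VAS is used, and in a PPP trial the patient may well take the condition to mean PPP. This mitigation is real if the request is made orally each time. It does not change what the form says, and a patient with two forms of psoriasis can read it either way.
- **The scale drawing is not in the text available here.** A printed label naming a site or period cannot be ruled out. This stands as a limit on the finding.
- **Rewording has a price.** Appendix VII cites a reliability and validity study of an itch VAS in psoriasis vulgaris (reference 39), and changed wording departs from it. This stands as a cost, although a source on psoriasis vulgaris lends no support to a hand-and-foot reading of the present wording.

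**Conclusion.** Both discrepancies are in the text. Appendix VII contradicts itself on the recall period, and its questions omit the site that the protocol specifies elsewhere. Some patients may therefore rate another period or symptoms beyond the hands and feet, and analysis cannot repair this afterwards. Severity is minor: the primary and secondary results are unaffected.

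A reader might infer more: that the scores do mix time frames, that patients with plaque psoriasis will rate the whole body, or that relief of body itch will be reported as a 6 to 12 mm benefit in PPP. The documents do not support this. They show ambiguous wording, not how patients answered; they direct investigators to hands and feet; and the SAP plans no report of the VAS. The 6 to 12 mm range also rests on an assumed prevalence, an assumed 30 mm fall in body itch, no change on hands and feet, and marks that follow body itch in full. It illustrates a possible shift and is not an estimate. The actual size cannot be derived from the documents.

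**What to change.** In Appendix VII and on the CRF:

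1. Change the marking instruction so that the mark reflects the average over the past week. This matches both questions and the seven-day period of the DLQI.
2. Add *on your hands and feet* to both questions. Alternatively, leave the questions as they are and place those words in a fixed heading, or in a scripted instruction read out before the patient marks the scale.

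The cost is a revision of one form and a note to sites, with no added burden for patients. Changing the questions departs slightly from the cited psoriasis itch VAS; the heading or script keeps the question wording intact. If patients have already used the present form, changing it partway would break comparability with their baseline. Keep each patient on one version and record which was used.
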